### 8.2 Statistical Analysis Plan (SAP)

Prior to database lock and before code breaking, a final version of the SAP shall be issued and approved by the study statistician, and the principal investigator. The SAP will define all "pre-specified, planned analyses" and provide the general specifications for the analysis of the data to be collected and presented in the Clinical Study Report.

### 9 Ethical principle

For every study site, only when the trial protocol is approved by the IRB, the enrollment of participant will begin, but all should be after May 1, 2019.

### 10 Funding

This study was supported and funded by the 2019 National Administration of Traditional Chinese Medicine "Project of building evidence-based practice capacity for TCM--Project BEBPC-TCM" (NO. 2019XZZX-ZJ) by China Academy of Chinese Medical Sciences.

### 12 Major update of the published protocol Important Changes Made to Study Design After Trial Commencement

No.	Item	Original version	Final version	Reason(s) for making change(s)
1	Exclusion criteria	(1)Patients diagnosed with clinically significant abnormal defecation due to functional disorders or structural abnormalities of the gastrointestinal tract and other tissues related to gastrointestinal tract (not including OIC)	with clinically significant abnormal defecation due to structural abnormalities of the gastrointestinal tract	To reconsider the appropriate exclusion for more enrollment
2	Exclusion criteria	(13)Patients that received an opioid receptor antagonist or agonist within one month of the screening, or those who are scheduled to receive such therapy during the study	an opioid receptor	the appropriate

4.4.3 Analyses for Primary Outcome	
4.4.4 Analyses for Secondary Outcome	
4.4.5 Safety Analyses	
5. The Summary of Changes of Final SAP	

1. Introduction

About 70-80% of patients experience moderate to severe pain. As the cornerstone of treatment for moderate to severe cancer pain, opiate analgesics, such as morphine and oxycodone, are recommended by WHO Cancer Pain Relief Guidelines. The use of systemic opioids is recommended by some studies for cancer patients experiencing moderate to severe pain, regardless of the underlying causes. Opioids stimulate receptors both in the central nervous system (CNS) and the peripheral nervous system, reducing pain and improving quality of life for patients. The drug can, however, be associated with serious adverse events (AEs) with a rate ranging from 1.8% to 13.6%, the most common of which is opioid-induced constipation (OIC). OIC represents a change in baseline bowel habits or defecation patterns that occurs following the administration or modification of opioid therapy. Approximately 41% of non-cancer patients and 94% of cancer patients who use opioids for pain have this condition. Symptoms of OIC are usually persistent and difficult to tolerate, which adversely affects patients' quality of life and results in reductions in dose or discontinuation of opioid analgesics. OIC is the result of multiple factors contributing to it: Opioids may activate μ-receptors throughout the gastrointestinal tract and cause changes to gut motility, decreases in gut secretion, and an increase in sphincter tone, which can lead to constipation. Various pharmacological and nonpharmacological interventions are used to manage OIC, such as laxatives and increased fluid intake. However, these interventions are limited in effectiveness, and they do not address the pathophysiological mechanisms of OIC. However, longer-term efficacy and safety of PAMORAs are unclear, and they haven't been approved in China yet. Clinical trials are still underway to test these drugs. Additionally, PAMORAs are often associated with AEs such as abdominal pain and flatulence. As a result, it is still necessary to explore new treatment approaches for OIC.

Acupuncture has been used to treat gastrointestinal disease, including constipation, for thousands of years. According to two systematic reviews, acupuncture can improve spontaneous bowel movements (SBMs) in functional constipation. Additionally, the results of our study indicated that electroacupuncture (EA) could increase complete spontaneous bowel movements (CSBMs) and SBMs, with a long-term effect that continues for 24 weeks after treatment ceased among patients with chronic, severe

functional constipation. Through stimulation of the somatic and peripheral nervous systems, acupuncture can facilitate the gut motility and improve gastrointestinal function. The effectiveness of acupuncture for OIC is currently lacking evidence.

2. Study objective

The objective of this study is to assess the efficacy of EA for OIC in adult patients with cancer pain.

3. Design

This is a multicenter, sham-controlled, assessor-blinded, randomized trial.

4. Statistical Considerations

4.1 Study Hypothesis

The primary study hypothesis is that EA is more effective than SA in patients with cancer pain.

4.2 Statistical Hypothesis

The null hypothesis is that the proportion of responders will be the same for EA and SA, and the alternative hypothesis is that the change would differ.

4.3 Study Populations

All patients with randomization will be included in the analysis set regardless of whether they receive any treatment. According to the intention-to-treat principle, all analysis will be based on the randomization set.

4.4 Statistical Analyses

4.4.1 The General Principle

Summary tables (descriptive statistics and/or frequency tables) will be provided for all variables at different endpoints. For continuous variables, means and standard deviations will be presented, unless the variable has a skewed distribution, in which case medians, 25th and 75th percentiles will be presented. For categorical variables, the number and percentage of participants within each category will be presented. For each variable (continuous or categorical), the number of missing values will be reported.

Statistical Comparisons Between Groups

Continuous variables will be compared using a two-sample *t*-test or Wilcoxon rank-sum test if data show serious deviations from a normal distribution. Categorical data or ordinal data will be compared using a Wilcoxon rank-sum test, chi-square test or Fisher's exact test, as appropriate. All tests will be two-sided.

For the analysis of the primary and secondary outcomes, estimated treatment differences and associated 95% two-sided confidence intervals will be presented.

Analysis Software

For all statistical analyses, SAS 9.4 software will be used. All hypothesis testing will be carried out at the 5% (2-sided) significance level.

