### 2.4.3 Trial flow chart

[figure not shown]
The trial flow chart was shown in Figure 2.

	Study Period				
	Baseline	Allocation	Treatment	Follow-up	
Enrollment	Weeks -1	Week 0	Weeks 1 to 8	Weeks 13 to 16	
Eligibility criteria	×				
Demography characteristics	×				
Disease history of cancer	×				
Disease history of OIC and constipation	×				
Eligibility screen	×				
Informed consent	×				
Allocation		×			
Interventions					
Electroacupuncture			×		
Sham electroacupuncture			×		
Assessments					
SBMs	×		×	×	
CSBMs	×		×	×	

Mean Bristol Stool Form Scale score for stool consistency of SBM	×	×	×
Mean score for straining of SBM	×	×	×
PAC-SYM total score and subscale scores	×	×	×
PAC-QOL total score and subscale scores	×	×	×
Patients' global assessment of treatment efficacy		X	×
Rescue medicine usage	×	×	×(weeks 9 -16)
Opioid usage	×	×	× (weeks 9-16)
Patients' expectation of the acupuncture efficacy	×		
Blinding assessment		X	
Cancer pain		×	×
Adverse events	×	×	× (weeks 9-16)
Safety assessment	×	×	× (weeks 9-16)

Abbreviations: OIC, Opioid-induced constipation; SBMs, spontaneous bowel movements; CSBMs, complete spontaneous bowel movements; PAC-SYM, Patient Assessment of Constipation-Symptom questionnaires; PAC-QOL, Patient Assessment of Constipation-Quality of Life questionnaires.

Figure 3. The schedule of enrollment, interventions, and assessments

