### 2.4.4.2 Secondary Outcomes

- (1) Changes in the mean weekly SBMs from the baseline during weeks 1-8 and weeks 13-16. The mean weekly SBMs equals the total frequency of SBMs divided by the numbers of week(s) recorded. Assessment time frame: at baseline, over weeks 1-8 and 13-16.
- (2) The proportion of patients with ≥3 mean weekly SBMs during weeks 1-8 and weeks 13-16. Assessment time frame: at baseline, over weeks 1-8 and 13-16.
- (3) The proportion of patients with an increase of ≥1 mean weekly SBM from the baseline during weeks 1-8 and weeks 13-16. Assessment time frame: at baseline, over weeks 1-8 and 13-16.
- (4) A change in the mean weekly CSBMs from the baseline during weeks 1-8 and weeks 13-16. A CSBM is defined as an SBM with the feeling of complete evacuation. The mean weekly CSBMs equals the total frequency of CSBMs divided by number of week(s)

recorded. Assessment time frame: at baseline, over weeks 1-8 and 13-16.

- (5) The proportion of patients with ≥3 mean weekly CSBMs during weeks 1-8 and weeks 13-16. Assessment time frame: at baseline, over weeks 1-8 and 13-16.
- (6) The proportion of patients with an increase of ≥1 mean weekly CSBM from the baseline during weeks 1-8 and weeks 13-16. Assessment time frame: at baseline, over weeks 1-8 and 13-16.
- (7) A change in the mean Bristol Stool Form Scale score for stool consistency of SBMs from the baseline during weeks 1-8 and weeks 13-16. For stool consistency, each patient will be asked to record their stool consistency according to the Bristol Stool Form Scale on the following seven points scale (scored from 1 to 7 for stool types 1 to 7, respectively). Assessment time frame: at baseline, over weeks 1-8 and 13-16.

- Type 1: Separate hard lumps, like nuts (hard to pass)
- Type 2: Sausage-shaped, but lumpy
- Type 3: Like a sausage but with cracks on its surface
- Type 4: Like a sausage or snake, smooth and soft
- Type 5: Soft blobs with clear cut edges (passed easily)
- Type 6: Fluffy pieces with ragged edges, a mushy stool
- Type 7: Watery, no solid pieces. Entirely liquid

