- (8) A change in the mean score for the straining of SBMs from the baseline during weeks 1-8 and weeks 13-16. For assessment of the straining of SBMs, each patient will be asked to rate his/her score of straining, using the following five-point scale: not at all difficult (0), a little bit difficult (1), moderately difficult (2), quite a bit difficult (3), extremely difficult (4). Assessment time frame: baseline, over weeks 1-8 and 13-16.
  - (9)A change in the total and subscale score of the Patient Assessment of

Constipation-Symptom (PAC-SYM) questionnaire from the baseline at weeks 8 and 16. The PAC-SYM is a questionnaire used to evaluate the severity of chronic constipation in the past 2 weeks. It consists of 12 items, which are subdivided into abdominal (4 items), rectal (3 items), and stool (5 items) scales.34 36 The score of each item ranges from 0 to 4, with 0 = symptom absent, 1 = mild, 2 = moderate, 3 = severe and 4 = very severe. Lower scores indicate a lower symptom burden. Each subscale score will be calculated as the mean of the completed items for that subscale. The total score will be calculated as the mean of all completed items. In this trial, the Chinese version of PAC-SYM, which has been validated to have a satisfactory psychometric property, will be used. Assessment time frame: at baseline, at weeks 8 and 16.

- (10) A change in the total and subscale scores of the Patient Assessment of Constipation-Quality of Life (PAC-QOL) questionnaires from the baseline at weeks 8 and 16. The PAC-QOL is a 28-item self-reported questionnaire to assess the burden of constipation on patients' everyday functioning and well-being in the 2 weeks (14 days) prior to assessment. This questionnaire is divided into four subscales: physical discomfort (items 1-4), psychosocial discomfort (items 5-12), worries/concerns (items 13-23), and satisfaction (items 24 to 28). Each of the item scores ranges from 0 (not at all) to 4 (extreme), with lower scores indicating a better quality of life. For each visit, individual subscale scores will be calculated as the mean of the completed items for that subscale. The total score will be calculated as the mean of all of the completed items. We will use the Chinese version of this test in our trial, which has been demonstrated to be a reliable and valid tool. Assessment time frame: at baseline, at weeks 8 and 16.

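### For change-from-baseline secondary outcomes analysed by t-test, baseline adjustment gives about equal or narrower 95% CIs at almost no cost; the Wilcoxon branch should stay and needs a matching estimate (optional)

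*SAP*

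**What the plan says.** Protocol 2.4.4.2 defines six secondary outcomes as changes from baseline. Four are compared over two windows: item (1), "Changes in the mean weekly SBMs from the baseline during weeks 1-8 and weeks 13-16"; item (4), "A change in the mean weekly CSBMs from the baseline during weeks 1-8 and weeks 13-16"; item (7), the mean Bristol score, over the same windows; and item (8), "A change in the mean score for the straining of SBMs from the baseline during weeks 1-8 and weeks 13-16". Two are questionnaire scores compared at two visits: item (9), PAC-SYM, and item (10), "PAC-QOL) questionnaires from the baseline at weeks 8 and 16". The schedule in Protocol 2.4.3 includes a baseline assessment for each of them, for example in the row "PAC-SYM total score and subscale scores".

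The comparison is set in SAP 4.4.1: "Continuous variables will be compared using a two-sample" t-test, or a "Wilcoxon rank-sum test if data show serious deviations from a normal distribution". For primary and secondary outcomes alike, the same section promises that "estimated treatment differences and associated 95% two-sided confidence intervals will be presented". SAP 4.4.4 adds the ITT population, no imputation and descriptive statistics, but no model. Neither document names the baseline value as a covariate for any of these outcomes.

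Protocol 8.1 also lists a repeated measures analysis among its options for secondary outcomes, without attaching it to any outcome. Protocol 8 refers to the SAP for details, and the SAP does not mention this analysis.

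**The concern.** A t-test on change scores estimates the treatment effect as the raw difference in mean change. That fixes the slope of follow-up on baseline at 1, whatever the data show. If the true slope is lower, as it is when the two SDs are similar and the correlation is moderate, the change score carries baseline noise that an adjusted analysis would remove. The baseline has already been collected, so the information is available and unused.

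In the Wilcoxon branch the gap is different. The SAP promises a difference and a CI, but does not say which estimate goes with the rank test.

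What is at stake is the precision and the definition of secondary estimates.

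**Working it through.** **Number analysed.** The documents give no sample size for these outcomes, so the number is taken from the primary calculation in Protocol 2.4.1.3: 14% response under sham, a difference of 31.4 points (so 45.4% under EA), 90% power, two-sided 0.05 and 20% loss. The unpooled two-proportion formula gives

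(1.960 + 1.282)² × (0.14 × 0.86 + 0.454 × 0.546) / 0.314² = 39.25 per arm.

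That is 40 per arm, 80 in total, and 80 / 0.8 = 100, which reproduces the stated 100. The check below uses N = 80 analysed.

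**Formulas.** Let s0 and s1 be the baseline and follow-up SDs, k = s0/s1, and ρ their correlation. The documents give none of these, so all values below are assumptions.

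- Variance of change: s1² × (1 + k² − 2ρk)
- Baseline-adjusted variance: s1² × (1 − ρ²)
- Difference between the two: s1² × (k − ρ)², which is never negative and is zero when ρ = k
- Large-sample variance ratio: R = (1 − ρ²) / (1 + k² − 2ρk)
- Cost of estimating the slope: a factor 1 + 1/(N − 4) on the variance, which is 1.013 at N = 80
- CI width ratio, ANCOVA to t-test: about √(R × 1.013), with a negligible change in the t quantile

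**Example.** With k = 1 and ρ = 0.5, R = 0.75 / 1.00 = 0.75, and √(0.75 × 1.013) = 0.87.

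**Results.** Variance ratio R, then CI width ratio:

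| Baseline SD / follow-up SD | ρ = 0.3 | ρ = 0.5 | ρ = 0.7 |
|---|---|---|---|
| 1 | 0.650; 0.81 | 0.750; 0.87 | 0.850; 0.93 |
| 0.75 | 0.818; 0.91 | 0.923; 0.97 | 0.995; 1.00 |
| 0.5 | 0.958; 0.99 | 1.000; 1.01 | 0.927; 0.97 |

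The worst case is ρ = k. There the adjusted interval is on average 0.7% wider at N = 80 and 0.5% wider at N = 100. Simulation with normal data (20,000 runs per setting) agreed with the formula, and coverage of the adjusted interval was 94.6% to 95.2%. These are averages over trials: in the worst case the adjusted interval was the narrower one in only about 20% of simulated trials, but the differences there are under 1%.

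**Seriously non-normal data.** Here the SAP would use Wilcoxon, so the fair comparator is the Hodges-Lehmann interval that belongs to that test, not a t-test interval. The settings simulated had 40 per arm, lognormal follow-up data and a pure shift, so that both methods target the same quantity. The ANCOVA interval with a heteroscedasticity-robust (HC3) standard error was wider than the Hodges-Lehmann interval in 15 of 18 settings (width ratio 0.86 to 2.19). A separate run gave 10 of 12 (0.84 to 2.19). Pairing a rank-based p-value with that mean-difference interval also led to contradictions: in about 16% to 32% of simulated trials the p-value was significant while the interval included zero. The lognormal is unbounded, whereas the Bristol, straining and PAC scores are bounded. These figures therefore show that a gain cannot be assumed; they do not predict this trial.

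**The case against.** The strongest reply is that the plan is already valid. Under randomisation an unadjusted comparison of change is unbiased, and a secondary outcome does not need the most efficient estimator. That stands, and it is why the point is optional. It does not show that the baseline is better left out: adjustment keeps every patient whom the change score keeps, since both need a baseline value.

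A second reply is that the gain is unproven here. That also stands in part. Without SDs or correlations, every percentage is conditional. The equal-SD row is the favourable end, because entry criteria select on constipation. Inclusion item (7) in Protocol 2.4.2.1 restricts baseline SBM frequency, so for SBM and CSBM the baseline SD may be well below the follow-up SD and the gain near zero.

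A reader might infer three stronger things, and the documents support none of them.

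- **That the planned tests are wrong or biased.** They are not.
- **That ANCOVA should replace both branches and would narrow all the intervals.** The SAP sends seriously skewed data to a rank test, and against the interval matching that test ANCOVA was wider in most of the shift settings examined.
- **That Protocol 8.1 and the SAP contradict each other on repeated measures.** Protocol 8.1 offers it as one of several options to be used where suitable and leaves the details to the SAP. Its absence from the SAP is missing detail.

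**Conclusion.** The point holds for the t-test branch only. For approximately normal data, a baseline-adjusted difference is about as precise as the raw difference in mean change, or more so. Its interval is 7% to 19% narrower if the two SDs are equal and the correlation lies between 0.3 and 0.7. It is 0% to 9% narrower if the baseline SD is three quarters of the follow-up SD, and within about 3% either way if it is half. The possible loss is about 0.7% in width. These figures assume 40 per arm, normal data and the stated range of correlations.

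For the Wilcoxon branch no gain in precision is claimed. What remains there is that the estimate and CI promised in SAP 4.4.1 have no named estimator. Overall this is a cheap, optional improvement to secondary estimates.

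**What to change.** Amend SAP 4.4.4 for the six change-from-baseline outcomes, keeping the SAP's existing rule for choosing between branches:

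1. Where the rule selects the t-test, use ANCOVA with the outcome's own baseline as covariate. Fit it separately for weeks 1-8 and weeks 13-16 (SBM, CSBM, Bristol, straining) or for weeks 8 and 16 (PAC-SYM and PAC-QOL, total and subscales). Take the difference, 95% CI and p-value from this one model.
2. Where the rule selects Wilcoxon, keep the Wilcoxon test on change and report the Hodges-Lehmann shift with its CI, so that test and interval rest on the same method. Do not pair a rank-based p-value with a mean-difference HC3 interval.
3. As a minor alignment, state which outcomes, if any, the repeated measures analysis in Protocol 8.1 covers.

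The cost is SAP wording, standard SAS code and one degree of freedom (about 1% of variance at 80 to 100 patients). No new data are needed.

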4.4.2 Demographics and Baseline Characteristics

All data recorded at baseline will be summarized by group. Comparisons between groups will be performed using the methodology described in section 4.4.1. Summaries will be presented for the ITT Set in both groups.

4.4.3 Analyses for Primary Outcome

The primary outcome will use a generalized linear model with a binomial distribution and identity link. The subgroup analysis will be conducted by adding an interaction between the baseline daily opioid dose and treatment into the generalized linear model

As a sensitivity analysis, missing data on the primary outcome will be imputed using the multiple imputation method under the missing at random assumption.

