### 2.4.1.1 Randomization

Web-based central randomization will be performed by the Linkermed Pharm Technology Co. Ltd (Beijing, China). Participants will be randomly allocated, in a 1:1 ratio, to either the EA or the SA group using permuted block-randomization. Acupuncturists in each center will be responsible for getting random numbers. Via inputting the screening information of the participant in the central randomization system through the web, they will get the random number and group allocation.

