### **2.4.1.3 Sample Size**

On the basis of unpublished data, a 14% response rate was assumed for the sham acupuncture group in this study. We estimated that a sample size of 100 participants would provide 90% power to detect a between-group difference of 31.4% at the two-sided significance level of 0.05 and 20% loss to follow-up.

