### 2.4.4 Outcomes Measurement

### 2.4.4.1 Primary Outcome

The primary outcome will be the the proportion of responders, defined as a patient that has  $\geq 3$  SBMs/wk and  $\geq$  increase of 1 SBM from baseline simultaneously for at least 6 out of 8 weeks of the treatment period. SBM refers to a bowel movement that occurred without medication or assistance within the previous 24 hours. When a bowel movement occurs within 24 hours of the use of an optional assisted method (rescue medication or other bowel-treatment regimens) for defecation, it is not regarded as an SBM.

[figure not shown]
Every participant will be required to keep a diary 13 weeks: baseline (run-out period before randomization), 8 weeks of treatment, and 4 weeks of follow-up. Diary entries include the frequency of bowel movements, the consistency of the stool, the difficulty in defecating, the rescue medicine drugs applied and their duration, and the intensity of the cancer pain. During the treatment period, the diary will be collected weekly, and during the follow-up period, it will be collected at the end of week 16. The outcome evaluators will examine the diary content and determine the SBM and frequency accordingly.

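### The SAP names no baseline covariate for the primary model; pre-specifying adjustment for baseline weekly SBM count could bring a small gain in precision

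*SAP*

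**What the plan says.** For the primary analysis, SAP section 4.4.3 says: "The primary outcome will use a generalized linear model with a binomial distribution and identity link". It gives a distribution and a link but no covariate list. The only baseline variable in that section is opioid dose, which enters in the subgroup analysis by "adding an interaction between the baseline daily opioid dose and treatment into the generalized linear model". Neither document mentions covariate adjustment of the primary outcome.

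Protocol section 2.4.4.1 defines a responder as a patient with at least 3 SBMs a week, and at least 1 more than baseline, in at least 6 of the 8 treatment weeks. The same section says "Every participant will be required to keep a diary 13 weeks: baseline", followed by the treatment and follow-up weeks. Protocol section 2.4.2.4 places the one-week baseline diary before randomization. Inclusion criterion 7 (protocol section 2.4.2.1) gives the SBM frequency off laxatives as 2 times a week in the text available to me, where a comparison sign may have been lost.

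Allocation is "in a 1:1 ratio, to either the EA or the SA group using permuted block-randomization", and no stratification factor is named, so the described design does not itself call for a covariate.

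**The concern.** Response depends on reaching 3 SBMs a week. A patient who starts at 2 is nearer that threshold than one who starts at 0, so the baseline count is an obvious candidate predictor. If it does predict response, adjusting for it removes the effect of chance imbalance and narrows the confidence interval without more patients or new data.

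The silence on covariates also matters a little in itself. SAP section 4.4.2 plans between-group comparisons of all baseline data. A generalized linear model with no stated covariate list leaves room to choose adjustment after an imbalance has been seen.

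**Working it through.** **Inputs from protocol section 2.4.1.3.** "We estimated that a sample size of 100 participants"; "a 14% response rate was assumed for the sham acupuncture group in this study"; "would provide 90% power to detect a between-group difference of 31.4" points; "two-sided significance level of 0.05 and 20% loss to follow-up". So p1 = 0.14 and p2 = 0.14 + 0.314 = 0.454.

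**Step 1: reproduce the plan's figure.** With the unadjusted, unpooled formula:

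n per arm = [p1(1−p1) + p2(1−p2)] × (1.960 + 1.282)² / (p2−p1)² = (0.1204 + 0.2479) × 10.507 / 0.0986 = 39.25, so 40.

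Total = 80 / (1 − 0.20) = 100, an exact match. Pooled variance would give 43 per arm and 108 in total; a continuity correction would give 49 per arm and 123 in total. The stated size therefore fits the unadjusted risk difference and does not rely on a covariate.

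**Step 2: unadjusted precision with 40 evaluable per arm.** SE = √(0.3683/40) = 0.096. The 95% half-width is 1.96 × 0.096 = 18.8 points. Power = Φ(0.314/0.096 − 1.96) = 90.5%.

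**Step 3: does the baseline clause of the definition bind?** If baseline is 0, 1 or 2, any week with 3 or more SBMs is already at least 1 above baseline. The clause is then redundant. The case for adjustment rests only on baseline being prognostic.

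**Step 4: effect of a given variance reduction.** Multiply the variance by (1 − R²). The documents give no R², so these values are assumed.

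| Assumed R² | Half-width (points) | Power |
|---|---|---|
| 0 | 18.8 | 90.5% |
| 0.02 | 18.6 | 91.1% |
| 0.05 | 18.3 | 91.9% |
| 0.07 | 18.8 × √0.93 = 18.1 | 92.4% |
| 0.15 | 17.3 | 94.4% |

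**Step 5: what reduction is plausible?** Simulation used 40 per arm, 14% versus 45.4%, an over-dispersed baseline count truncated at 2, eight Poisson weeks and 6,000 trials per scenario.

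- Improvement adds a similar number of SBMs whatever the baseline (5 scenarios): variance ratio 0.993–1.004; power 0.894–0.903 unadjusted, 0.893–0.901 adjusted.
- Improvement is proportional to baseline (4 scenarios): variance ratio 0.931–0.980; power 0.889–0.900 unadjusted, 0.895–0.916 adjusted, a gain of 0.6–1.9 points.
- Type I error: 4.9–5.7% adjusted, 5.2–5.6% unadjusted.

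A further set of runs under the same design gave variance ratios of 0.93–1.00, power 0.2–1.8 points higher, and type I error of 5.2–5.8% adjusted against 4.9–5.9% unadjusted.

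A different model assumed a baseline mix of 0/1/2 = 30/40/30% and a fixed odds ratio of response per extra baseline SBM (4,000 runs per setting). Variance ratios were 1.01, 1.00, 0.97 and 0.91 for odds ratios of 1, 1.5, 2 and 3. A reduction beyond 7% thus needs an odds ratio of about 3 for a single extra SBM in one week.

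**Step 6: adding the covariate to the identity-link model.** With the same 30/40/30% mix, 500 runs per setting and constrained maximum likelihood:

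| Odds ratio | Fitted risk on the boundary (0 or 1) | SD of estimate, adjusted vs unadjusted |
|---|---|---|
| 1 | 17% | 0.095 vs 0.095 |
| 1.5 | 31% | 0.094 vs 0.094 |
| 2 | 41% | 0.103 vs 0.102 |
| 3 | 61% | 0.096 vs 0.094 |

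This route brings no fall in the SD and a frequent boundary problem.

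**The case against.** The strongest reply is that nothing in the plan is wrong. The unadjusted risk difference is valid under 1:1 randomization, the identity link gives directly the difference and interval promised in SAP section 4.4.1, and the sample size matches that analysis. In the additive scenarios adjustment gains nothing, and no passage shows that baseline SBM count predicts response. This stands, and it keeps the point at the level of an optional improvement.

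It can also be said that adjustment is not free. In the fixed-odds-ratio runs, rejection under the null was 5.2–5.6% adjusted against 4.7–5.1% unadjusted. The simulation error there is about 1.96 × √(0.05 × 0.95/4,000) = 0.7 points, and the other runs show no consistent excess. This part does not count against the change.

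The procedural objection has some weight. SAP section 5 records that the primary method has already moved from a chi-square test to this model, and the opioid-dose interaction is defined on it.

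Three stronger readings are tempting. A reader might infer that the SAP specifies treatment alone; it is silent, and treatment alone is only the natural reading. A reader might infer that baseline must matter because it appears in the responder definition; with a baseline of at most 2 that clause never decides anything. A reader might infer that the trial is short of power; the stated 90% is reached without adjustment.

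**Conclusion.** The point holds as a minor efficiency improvement. No covariate is named for the primary model, and a plausible one is already collected before randomization. The expected benefit is about 0–7% less variance, equivalent to at most about 0.7 points off an 18.8-point half-width, and about 0–2 points of power.

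This rests on two assumptions that the documents do not settle: that criterion 7 is an upper limit of 2 SBMs per week, and that the link between baseline and response lies in the simulated range. If every patient enters at exactly 2, the covariate is constant and the gain is nil. Larger gains, such as the 94.4% power at R² = 0.15, need a stronger association than the documents give reason to expect.

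**What to change.** In SAP section 4.4.3:

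- Fit a logistic model with treatment and baseline weekly SBM count. Estimate the risk difference by standardisation: average over all randomized patients the predicted risk under EA minus the predicted risk under SA. Give a robust 95% confidence interval. This targets the same marginal risk difference as the current model.
- Keep the unadjusted identity-link model as a sensitivity analysis, and do not add the covariate to it.
- State which of the two models carries the opioid-dose interaction.
- Check the wording of inclusion criterion 7 first, because the gain depends on the true range of baseline counts.

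If the sponsor prefers no adjustment, one sentence saying that the primary model has no baseline covariate would close the gap.

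The cost is a short passage of SAP text and a few lines of code, with no new data. It is also a second change to the primary method, to be recorded in SAP section 5 and made before database lock and code breaking, the limit that protocol section 8.2 sets for the final SAP.
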